7.5. Endpoints Based on Patient-reported Outcomes

The following patient-reported outcomes will be assessed and data listings will be provided. Analyses involving baseline value will be based on study 9HB01EXT Baseline (as defined above in Section 5.1.2). Questionnaires taken during major surgical/rehabilitation periods will not be included in the analyses but are flagged in the listings. In addition, age restriction at the entry into study 9HB01EXT will be applied for summary tables and flagged in the listings for those questionnaires as shown below:

Questionnaire	Age restriction at entry to 9HB01EXT
For subjects from study 998HB102 only:	
HAEMO-QoL	≥ 13 to ≤ 16 years old

HAEM-A-QoL	≥17 years old
EQ-5D-L	≥18 years old
For subjects from study 9HB02PED only:	
CHO-KLAT	≥5 years old
EQ-5D-Y	≥7 years old

7.5.1. HAEMO-QoL and HAEM-A-QoL

The questionnaires will be analyzed according to the recommendations of the questionnaire authors (see <http://www.haemoqol.de>). Details of the questionnaire are provided in Appendix CC.

The algorithm for deriving the sub scores is given in Appendix C.

The HAEMO-QoL questionnaire for Children and Teenagers aged 13-16 contains 12 sub-grouped sections, which will count as 12 separate sub-scores. Further details on the sub-scores are contained in Appendix CC. The following sub-sections make up the 12 sub-scores of the HAEMO-QoL questionnaire:

Time Period	Sub-scores for HAEMO-QoL
During the past month	1. Physical health 2. Feeling 3. View of yourself 4. Family 5. Friends 6. Perceived support 7. Others persons 8. Sports and school 9. Dealing with hemophilia 10. Treatment 11. Future 12. Relationships

The HAEM-A-QoL questionnaire for Adults contains 10 sub-grouped sections, which will count as 10 separate sub-scores. The following sub-sections make up the 10 sub-scores of the HAEM-A-QoL questionnaire:

Time Period	Sub-scores for HAEM-A-QoL
During the past month	1. Physical health 2. Feeling of yourself 3. View 4. Sports and leisure 5. Work and school 6. Dealing with hemophilia 7. Treatment
Recently	8. Future 9. Family planning 10. Partnership and sexuality

As specified in Appendix C, questions will either have been coded or will be re-coded to ensure that high scores represent a low quality of life and low scores represent a high quality of life. These scores are then transformed to produce a Transformed Scale Score (TSS). This score is

scaled, as a percentage, from 0 to 100%, with higher TSS values representing a worst quality of life for each sub-score and total score summary measurement.

For both the HAEMO-QoL and HAEM-A-QoL questionnaires the total scores and individual sub-scores based on the TSS will be summarized by visit for overall treatment regimen and change from study 9HB01EXT baseline at each visit for the FAS.

7.5.2. Hemo-Sat Patient Satisfaction Scale

A copy of the questionnaire and further details on the subscales and the calculation of the subscores are contained in Appendix F.

As specified in Appendix F, questions will either have been coded or will need to be re-coded to ensure that high scores represent a low satisfaction and low scores represent a high satisfaction. These scores are then transformed to produce a Transformed Scale Score (TSS). This score is scaled as a percentage from 0 to 100% for each sub-score and total score, with higher TSS values representing a worst satisfaction.

The total score and individual subscores based on the TSS will be summarized for the observed response and change from baseline using descriptive statistics for the FAS. A negative change from baseline represents an improvement in satisfaction. Summaries will be at each visit. See Section 5.1.4 for details of when questionnaire results should be excluded from tabulated summaries.

7.5.3. CHO-KLAT

Two forms of the assessment tool were administered for subjects from 9HB02PED, one to the subjects (Child Self-report Questionnaire), and one to the parent/caregiver (Parent/Proxy Questionnaire).

A copy of the questionnaires and details on their scoring are provided in Appendix E. As specified in Appendix E, questions will either have been coded or will need to be re-coded to ensure that high scores represent a high quality of life and low scores represent a low quality of life. These scores are then transformed to produce a Transformed Scale Score (TSS). This score is scaled, as a percentage, from 0 to 100%, with higher TSS values representing a better quality of life.

The total score based on the TSS will be summarized for the observed response and change from study 9HB01EXT baseline using descriptive statistics. A positive change from baseline represents an improvement in quality of life. Summaries will be at each visit. See Section 5.1.4 and Appendix E for details of when questionnaire results should be excluded from tabulated summaries.

7.5.4. EQ-5D Youth Questionnaire

The EQ-5D™ is a standardized instrument used to measure health outcome. EQ-5D-Y is a version of this instrument developed for use in children and adolescents.

The questionnaire will be analyzed according to the recommendations of the authors (see www.euroqol.org). EQ-5D-Y consists of 2 pages – a 5 dimension descriptive system and the EQ visual analogue scale. The elements of the questionnaire are provided in Appendix G.

The descriptive system contains 5 categories: mobility; looking after myself; doing usual activities; having pain or discomfort; and feeling worried, sad, or unhappy. Each category has 3 levels of response representing no problems, some problems, and a lot of problems.

The EQ visual analogue scale is a visual scale from 0 to 100 used to record a subject's overall self-rated health state. The subject is asked to mark an 'X' on the scale then record the corresponding number; 0 refers to the worst possible health state, 100 refers to the best possible health state.

The EQ visual analogue scale will be summarized for the observed response and change from study 9HB01EXT baseline using descriptive statistics for the FAS. Summaries will be provided by visit for overall treatment regimen. See Section 5.1.4 for details of when questionnaire results should be excluded from tabulated summaries.

7.5.5. EQ-5D-3L Questionnaire

The questionnaire will be analyzed according to the recommendations of the authors (see www.euroqol.org). EQ-5D consists of 2 pages – a 5 dimension descriptive system and the EQ visual analogue scale. A copy of the questionnaire is provided in [Appendix D](#).

The descriptive system contains 5 categories: mobility, self-care, usual activities, pain/discomfort and anxiety/depression. The number and percentage of subjects in each response category were tabulated for the FAS. Percentages are based on the number of subjects for whom an assessment is provided at the respective visit.

The EQ visual analogue scale is a visual scale from 0-100 to record a respondent's overall self-rated health state. The respondent is asked to mark an 'X' on the scale then record the corresponding number; 0 refers to the worst possible health state, 100 refers to the best possible health state. This will also be presented alongside the 5 dimension descriptive system scores.

The EQ visual analogue scale will be summarized for the observed response and change from the study 9HB01EXT baseline by visit for overall for the FAS. See Section 5.1.4 for details of when questionnaire results should be excluded from tabulated summaries.

7.5.6. Health-Economic Parameters

Health-economic assessments consist of the following items based on the time period since the last visit at which they were assessed:

- Number of hospitalizations excluding planned hospitalizations, elective surgery documented at Visit 1, and emergent surgery
- Number of emergency room visits
- Number of physician visits, excluding study visits
- Number of hospitalization days
- Number of days off work, school, day care, or preschool
- Number of days off work for the parent or caregiver

The previous visit for the Visit 1 refers to the previous visit in the parent study where applicable.

These data will be tabulated categorically at each visit for overall treatment regimen for the FAS. Information collected on the questionnaire relates to both hemophilia and non-hemophilia related events. Thus, in addition to summarizing the hemophilia-related health resource utilization, the utilization for hemophilia- and non-hemophilia related events will be combined and the total summarized for the last 4 assessments listed above.

7.6. Surgery Data

Due to the small overall size of the Surgery Subgroup as described in Section 4.4, efficacy analyses will predominantly be based on assessment of subject data listings.

The following information will be provided in the data listings:

- Dates/times for the various components of the surgical rehabilitation period (hospital admission, surgery, and discharge)
- The surgical procedure performed, blood loss, and drainage
- Blood products used including details for type of transfusion, date/time administered, and amount given
- Surgeon's/Investigator's assessment of hemostatic response to rFIXFc
- Dosing during surgery, on the day of surgery, and for the first 14 days post-surgery (Days 1-3, Days 4-14, and Days 1-14)
 - during surgery: number of injections, average dose per injection, and total dose required to maintain hemostasis
 - day of surgery: total dose required to maintain hemostasis
 - post-surgery: total rFIXFc administered, the total number of injections, and the minimum and maximum intervals of time between injections
- The number of injections required to maintain hemostasis and average daily dose on the day of surgery and for Days 1-3 and Days 4-14 following surgery
- Injections and bleeding episodes during surgery and for the first 14 days following surgery, FIX levels, reason for injection, nominal dose, hours since the last injection, and if any additional treatment was given to treat the bleed

The following information will be summarized for the FAS:

- Number of injections and mean and total dose per injection required to maintain hemostasis during the major surgical period
- Estimated blood loss during major surgery
- Total rFIXFc consumption (IU/kg) per major surgery
- Number of bleeds after surgery per major surgery

In addition, minor surgeries will be summarized and listed where possible in a similar manner for the FAS.

During surgery includes the pre-surgery dose given for the surgery. The day of surgery refers to the calendar day of the surgery and includes the pre-surgery dose given for the surgery, even if it was given on the previous day. Day 1 refers to the day following surgery. The average dose per injection will be determined as the average dose across all injections during the referenced time period. Total dose will be determined as the sum of all doses administered during the referenced time period.

7.6.1. Investigators'/Surgeons' Assessment of Hemostatic Response to Surgery Using the 4-point Bleeding Response Scale

The Investigators'/Surgeons' assessment (using the 4-point surgery response scale detailed in Appendix B) of the subject's hemostatic response to rFIXFc within 24 hours post-surgery will be summarized categorically for all major surgeries for the FAS. Categorically, the number and percentage of surgeries given each rating will be tabulated. Percentages will be based on the number of surgeries for which a response was provided.

The above data will be summarized as follows:

- For subjects from study 998HB102, the data will be summarized overall for the surgery subgroup in 9HB01EXT.
- For subjects from study 9HB02PED, the data will be summarized by age cohort for the surgery subgroup in 9HB01EXT.

Subjects will not be included in the surgery subgroup for a minor surgery. Data from minor surgeries from all subjects will be summarized and listed in the same format as used for major surgeries.

7.7. Pharmacokinetic Assessments

FIX activity levels data will be provided in a listing.

8. SAFETY ANALYSIS

Safety data will be summarized for subjects from study 9HB02PED and subjects from study 998HB102, along with the overall total. The analysis population for safety analyses is defined in Section 4.3.

Adverse events (AEs) will be summarized for subjects from each parent study and overall for all subjects in study 9HB01EXT, regardless of treatment arm for subjects from study 998HB102, age cohort for subjects from study 9HB02PED, and treatment regimen in study 9HB01EXT.

In addition, all data from study 9HB01EXT will be provided in data listings.

8.1. Primary Endpoint

The primary safety endpoint is the occurrence of inhibitor development as determined from the Nijmegen-modified Bethesda assay. A listing of inhibitor test results will be provided.

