Endpoints for patient-reported outcomes (Haem-A-QoL, Haemo-QoL, Hemo-Sat-Patient, CHO-KLAT Children, CHO-KLAT Proxy, EQ-5D-Y and EQ-5D-3L) will be analyzed in a separate report. These endpoints will be analyzed by summarizing actual values and changes from baseline, as appropriate.

Summary statistics of health outcome endpoints will be tabulated at each collection timepoint.

Safety

The Safety Analysis Set will include all subjects with at least one dose of rFIXFc. For the analysis of safety, data in 9HB01EXT will be integrated with data from the parent studies, unless specified otherwise. The incidence of adverse events (AEs) will be tabulated overall, by severity, and by relationship to treatment. In addition, the incidence of AEs will be presented by ED intervals. Findings in clinical lab values will be summarized by descriptive statistics.

The proportion of subjects with inhibitors during rFIXFc administration will be provided with the exact (Clopper-Pearson) 2-sided, 95% confidence interval.

Interim Analysis:	Interim analyses will be conducted during the study, as needed. Analyses will be descriptive in nature. No formal comparisons are planned and no hypotheses will be formally tested. The study has an open label design and thus, personnel conducting interim analyses will not be blinded to treatment assignments.
Sample Size Determination:	This is an extension study. The samples size is based on sample sizes of studies 998HB102, and 9HB02PED and is estimated to be approximately 120 subjects, but may be increased based upon subject participation in other rFIXFc studies.
Study Stopping Rules:	The Sponsor may terminate this study at any time, after informing Investigators.

CONFIDENTIAL

The information contained herein may not be used, disclosed, or published without the written consent of Biogen Idec MA Inc.

Study stopping is required if any of the following occur:

- Three subjects develop a high-titer inhibitor (i.e. ≥ 5.00 BU/mL), identified and confirmed on 2 separate samples drawn approximately 2 to 4 weeks apart, and performed by the central laboratory using the Nijmegen-modified Bethesda assay. This number can be adjusted based on sample size when more subjects might be included into this trial from other rFIXFc studies.
- An unexpected, serious, or unacceptable risk to study subjects.

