16.6.2. Methods of Analysis

For the analysis of safety, data in 9HB01EXT will be integrated with the parent study data, unless specified otherwise. The incidence of AEs will be tabulated overall, by severity, and by relationship to treatment. In addition, the incidence of AEs will be presented by exposure day (ED) intervals. An ED is a 24-hour period, in which one or more rFIXFc injections are given.

CONFIDENTIAL

The information contained herein may not be used, disclosed, or published without the written consent of Biogen Idec MA Inc.

Subject listings will be provided for all AEs, SAEs, AEs resulting in discontinuation of the study treatment or withdrawal from the study, and death. Findings for clinical lab values will be summarized by descriptive statistics. Listings of vital signs and abnormal laboratory test results will be provided.

The total number of EDs of rFIXFc will be summarized by treatment regimen and overall for 9HB01EXT, and overall using combined data from the parent studies and 9HB01EXT.

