16.7.2. Methods of Analysis

The proportion of subjects with an inhibitor during rFIXFc administration will be provided with the exact (Clopper-Pearson) 2-sided, 95% confidence interval. Any subject with an inhibitor (as defined in section 7.1.2) following the initial rFIXFc administration, will be counted in the numerator; however, only subjects who have completed at least 50 EDs, and 100 EDs from their initial rFIXFc administration, will be included in the denominator. Unless all subjects complete at least 50 EDs, the proportion of subjects with an inhibitor will also be calculated using all subjects, regardless of the amount of exposure to rFIXFc, in the denominator.

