5. DATA HANDLING

This study is being conducted under the sponsorship of Biogen. Data management is being performed under contract with Quintiles in collaboration with Bioverativ. Statistical analysis is being performed by Biogen, using SAS[®] version 9.3 or higher and, where appropriate, additional validated software. This statistical analysis plan (SAP) is based on protocol Version 4, dated 13 November 2013 and will detail analyses to be performed and summaries to be produced for the final Clinical Study Report (CSR).

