8.3.2. Inhibitor Development

Inhibitor results of the Nijmegen-modified Bethesda Assay from the central laboratory will be listed. Results from blood samples collected during surgical/rehabilitation periods for the purpose of determining the presence of an inhibitor will be included.

A positive inhibitor occurs where a subject has a value ≥ 0.6 Bethesda Units (BU/mL) confirmed on re-testing between 2 and 4 weeks later. Both tests must be performed by the central laboratory.

A “low” titer inhibitor occurs where a subject has a value between 0.6 and <5.0 Bethesda Units (BU/mL) confirmed on re-testing between 2 and 4 weeks later.

A “high” titer inhibitor occurs where a subject has a value ≥ 5.0 Bethesda Units (BU/mL) confirmed on re-testing between 2 and 4 weeks later.

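### For the only primary endpoint, inhibitor development, the SAP plans listings alone; the protocol's proportion with exact 95% CI is missing, and the SAP's exposure-day count cannot supply its denominators.

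*SAP*

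**What the plan says.** Protocol 16.7.2 sets the analysis: "The proportion of subjects with an inhibitor during rFIXFc administration will be provided with the exact (Clopper-Pearson) 2-sided, 95% confidence interval". The synopsis repeats it: "The proportion of subjects with inhibitors during rFIXFc administration will be provided with the exact (Clopper-Pearson) 2-sided, 95% confidence interval". Under 16.7.2, any inhibitor after the first rFIXFc administration counts in the numerator, but "only subjects who have completed at least 50 EDs, and 100 EDs from their initial rFIXFc administration, will be included in the denominator". I read this as two denominators, one per ED threshold. A third is conditional: "Unless all subjects complete at least 50 EDs, the proportion of subjects with an inhibitor will also be calculated using all subjects". Protocol 16.6.2 also wants total EDs summarized "overall for 9HB01EXT, and overall using combined data from the parent studies and 9HB01EXT".

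The SAP declares its basis in section 5: "This statistical analysis plan (SAP) is based on protocol Version 4, dated 13 November 2013 and will detail analyses to be performed". On the primary endpoint, SAP 8.1 says: "A listing of inhibitor test results will be provided". SAP 8.3.2 says: "Inhibitor results of the Nijmegen-modified Bethesda Assay from the central laboratory will be listed". It then defines positive, low-titer and high-titer results and includes samples from surgical/rehabilitation periods. The SAP's list of tables has no inhibitor table, and its list of listings has one entry for inhibitor results. SAP 1 and 5.1 restrict data and listings to 9HB01EXT. SAP 7.3.2 counts EDs from the start of the first extension regimen.

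**The concern.** The study is descriptive and tests no hypothesis (protocol 16), so the inhibitor proportion and its interval are the whole planned result for the primary endpoint. A report that follows the SAP would show inhibitor results line by line. It would not give the protocol's estimate, the risk that the data can exclude, or the risk among subjects with 50 or 100 EDs. By contrast, the anti-rFIXFc antibody assay, which protocol 7.1.3 calls exploratory, gets counts, percentages and a table (SAP 8.3.3 and list of tables).

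**Working it through.** **1. Planned size.** Protocol 16.10 and SAP 3.3.1 give 100 subjects from 998HB102 and 20 from 9HB02PED: 100 + 20 = 120, matching the stated figure of about 120. No precision target is stated.

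**2. Search for the analysis.**

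| Item | Protocol 16.7.2 | SAP 8.1, 8.3.2 and output lists |
|---|---|---|
| Proportion | yes | none |
| Exact 95% CI | yes | none |
| Denominator: at least 50 EDs since first rFIXFc | yes | none |
| Denominator: at least 100 EDs since first rFIXFc | yes | none |
| All subjects (conditional) | yes | none |
| Listing | not mentioned | yes |

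**3. Intervals not reported.** The Clopper-Pearson limits for x cases in n are beta quantiles: lower = B(0.025; x, n−x+1), upper = B(0.975; x+1, n−x). With x = 0 the upper limit is 1 − 0.025^(1/n). The documents give no extension-study results, so the case counts are illustrative.

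| n | 0 cases, upper limit | 1 case (95% CI) | 2 cases (95% CI) |
|---|---|---|---|
| 120 (all) | 3.03% | 0.83% (0.02 to 4.56) | 1.67% (0.20 to 5.89) |
| 100 (998HB102) | 3.62% | 1.00% (0.03 to 5.45) | 2.00% (0.24 to 7.04) |
| 20 (9HB02PED) | 16.84% | 5.00% (0.13 to 24.87) | 10.00% (1.23 to 31.70) |

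If only 90 or 60 of the 120 reached 100 EDs (an assumption), the zero-case upper limit would be 4.02% or 5.96%.

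**4. Exposure-day offset.** Protocol 16.7.2 counts from the first rFIXFc dose; the SAP starts at zero on entry to the extension.

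- 9HB02PED: completers are planned to have at least 50 EDs (protocol 5.1.3). The 20 or so expected would meet the 50-ED criterion at entry, while the SAP's variable gives them 0.
- 998HB102, weekly regimen only, as an illustration: 26 or 52 parent-study weeks give about 26 or 52 EDs. If weekly dosing continues, 100 cumulative EDs are reached after 100 − 26 = 74 or 100 − 52 = 48 extension weeks, against 100 weeks on the SAP's count.

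**5. Numerator and denominator.** As protocol 16.7.2 is written, a subject with an inhibitor before reaching 50 EDs enters the numerator but not the denominator. The ratio is then not a binomial proportion, and the exact interval does not strictly apply. Suppose 110 subjects pass the cut-off and the one case lies below it (assumed). As written the result is 1/110 = 0.91% (0.02 to 4.96). With the case added to the denominator it is 1/111 = 0.90% (0.02 to 4.92). The numerical difference is small here.

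**The case against.** The strongest reply is that little information is lost.

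- **Cases are visible.** Every central-laboratory inhibitor result in the extension is listed. Confirmed inhibitors must be reported as SAEs (protocol 15.2.3), and treatment-emergent SAEs are tabulated with Safety Analysis Set percentages (SAP 8.2.2, 8.2.6). A case arising in the extension would therefore normally appear with a crude percentage. This stands, with limits. SAP 8.2.1 keeps events from major surgical/rehabilitation periods out of every AE table except the overall summary, and the SAE table has neither a CI nor an ED denominator.
- **The scope was declared.** SAP 1 states that only extension data are used, and protocol 16.6.2 integrates safety data unless specified otherwise. A reader might infer that extension-only scope itself contradicts the protocol; it does not. But scope does not explain dropping the proportion and interval, since extension-onset cases among all subjects could be summarized from extension data alone. Protocol 16.7.2 attaches no such exception to its ED denominators.
- **EDs are tabulated.** SAP 7.3.2 does use categories split at 50 and 100 EDs, but on extension exposure only. SAP 3.1 itself describes the 100-ED follow-up expectation as a total across parent and extension studies.

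Two stronger inferences fail. First, a reader might apply the 26 or 52 EDs to all 998HB102 subjects as a minimum, because protocol 5.1.3 reports 115 of 123 treated for at least 26 weeks and 56 for at least 52. Those counts include individualized-interval and on-demand subjects. Dosing every 14 days, for example, would give about 13 or 26 EDs. Second, a reader might conclude either that inhibitor cases go unreported or that none can be missed. Extension-onset cases are reported. Inhibitors confirmed in a parent study, which protocol 16.7.2 counts, fall outside the SAP's data.

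**Conclusion.** The omission is real and should be corrected before the final analysis. The SAP replaces the protocol's analysis of the only primary endpoint with listings and records no reason. Its ED variable cannot produce the 50-ED and 100-ED denominators, or the combined ED total in protocol 16.6.2.

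The loss is one of estimation and conformity with the protocol, not of case detection within the extension. At the planned sizes, the missing zero-case upper limits run from 3.03% overall to 16.84% in the pediatric group. These figures assume that planned enrolment is met; the numbers reaching each ED threshold are not in the documents.

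Under this SAP, parent-study cases could come only from 9HB02PED. SAP 4 admits only the two named parent studies, protocol 5.1.3 reports no inhibitor in 998HB102, and the entry criteria exclude only confirmed high-titer inhibitors. The documents do not say whether any such case exists.

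**What to change.** Add one inhibitor incidence table to SAP 8.1/8.3.2 and the list of tables:

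- number of cases, denominator, proportion and Clopper-Pearson two-sided 95% CI, overall and by parent study;
- the protocol 16.7.2 denominators: at least 50 EDs, at least 100 EDs, and all subjects unless everyone reaches 50 EDs;
- EDs counted cumulatively across parent and extension studies, which also supplies the combined total in protocol 16.6.2;
- surgical/rehabilitation samples included, as SAP 8.3.2 already does for the listing;
- cases first confirmed in the extension shown separately from any confirmed in the parent study;
- alongside the protocol version, a version that adds cases below the ED cut-off to the denominator, so that the binomial interval is valid.

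If the sponsor does not want this analysis, the SAP should record it as a change from protocol 16.7.2 and give the reason.

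Cost: one SAP revision, one table, and a merge of existing parent-study dosing and inhibitor records. No new data collection is needed.
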